6.1.2 Post Baseline Period

On-treatment AEs will be defined as AEs with an onset date-time on or after the date-time of the first dose of study treatment (or with an onset date on or after the day of first dose of study treatment if time is not collected or is missing). An AE will be counted as on-treatment if the event occurred within 30 days (or 100 days depending on analysis) of the last dose of study treatment.

On-treatment evaluations (laboratory tests, pulse oximetry and vital signs) will be defined as evaluations taken after the day (and time, if collected and not missing) of first dose of study treatment. An evaluation will be counted as on-treatment if it occurred within 30 days (or 100 days depending on analysis) of the last dose of study treatment.

The Post Baseline Period may be further divided into the following sub-periods.

6.1.2.1 Part 1 Treatment Period (Combination Portion)

Part 1 dosing is defined as any medication recorded on 'Record of Study Medication' CRF page with a visit label containing the text 'Part 1' and with total volume infused > 0 mL.

On-treatment AEs during the Part 1 Treatment Period will be defined as AEs with an onset date-time on or after the date-time of the first dose of Part 1 study treatment (or with an onset date on or after the day of first dose of Part 1 study treatment if time is not collected or is missing). An AE will be counted as on-treatment during Part 1 if the event occurred within 30 days (or 100 days depending on analysis) of the last dose of Part 1 study treatment.

On-treatment evaluations (laboratory tests) during Part 1 will be defined as evaluations taken after the day (and time, if collected and not missing) of first dose of Part 1 study treatment. An evaluation will be counted as on-treatment during Part 1 if it occurred within 30 days (or 100 days depending on analysis) of the last dose of Part 1 study treatment.

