4.5 Selection and Timing of Dose for Each Subject

The dosing regimen and schedule for Parts 1 and 2 are detailed in Table 4.5-1 and Table 4.5-2, respectively.

Note: The first flat dose 480 mg nivolumab in Part 2 will be administered 6 weeks after the last combination dose in Part 1.

Table 4.5-1: Dosing Schedule for Part 1 (Double-Blinded)				
Every 3 weeks dosing 1 cycle = 3 weeks				
	Cycle 1	Cycle 2	Cycle 3	Cycle 4
Arm A	Nivolumab 3 mg/kg Ipilimumab 1 mg/kg	Nivolumab 3 mg/kg Ipilimumab 1 mg/kg	Nivolumab 3 mg/kg Ipilimumab 1 mg/kg	Nivolumab 3 mg/kg Ipilimumab 1 mg/kg
Arm B	Nivolumab 1 mg/kg Ipilimumab 3 mg/kg	Nivolumab 1 mg/kg Ipilimumab 3 mg/kg	Nivolumab 1 mg/kg Ipilimumab 3 mg/kg	Nivolumab 1 mg/kg Ipilimumab 3 mg/kg

Table 4.5-2: Dosing Schedule for Part 2 (Open Label)	
Every 4 weeks dosing 1 cycle = 4 weeks, Cycle 5 to begin 6 weeks after Cycle 4 ^a	
	Cycle 5 and beyond
Arms A and B	Flat dose 480 mg nivolumab

^a Cycle X - Cycle 8, 9, etc until disease progression or unacceptable toxicity or a maximum treatment of 2 years.

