4 ENDPOINTS

4.1 Primary Endpoint: Rate of Drug-related Grade 3-5 AEs

The primary endpoint of the study is the rate of drug-related Grade 3 - 5 adverse events in Arms A and B. The drug-related Grade 3 - 5 AE rate is defined as number of subjects who experienced at least 1 AE of Grade 3 or higher, judged to be related to study drug by the investigator, and with onset on or after the first dose of study treatment and within 30 days of the last dose of study treatment, divided by number of treated subjects. AE grade will be defined using National Cancer Institute Common Terminology Criteria for Adverse Events (NCI CTCAE) version 4.0 criteria.

The analysis of the primary endpoint will occur when all treated subjects who are still on-treatment have had at least 2 post-baseline tumor assessments.

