6.1.2.2 Part 2 Treatment Period (Maintenance Portion)

Part 2 dosing is defined as any medication recorded on 'Record of Study Medication' CRF page with a visit label containing the text 'Part 2' and with total dose delivered > 0 mg.

On-treatment AEs during the Part 2 Treatment Period will be defined as AEs with an onset date-time on or after the date-time of the first dose of Part 2 study treatment (or with an onset date on or after the day of first dose of Part 2 study treatment if time is not collected or is missing). An AE will be counted as on-treatment if the event occurred within 30 days (or 100 days depending on analysis) of the last dose of Part 2 study treatment.

On-treatment evaluations (laboratory tests) during Part 2 will be defined as evaluations taken after the day (and time, if collected and not missing) of first dose of Part 2 study treatment. An evaluation will be counted as on-treatment if it occurred within 30 days (or 100 days depending on analysis) of the last dose of Part 2 study treatment.

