7.6 Safety

7.6.1 Rate of Drug-related Grade 3-5 AEs

For purposes of the primary endpoint analysis, the drug-related Grade 3 - 5 AE rate for All Treated Subjects in Arms A and B will be reported by treatment arm. Corresponding 95% CIs for the rate

in each treatment arm will be calculated using the Clopper-Pearson method. A p-value from a two-sided CMH test stratified by PD-L1 status and M Stage at screening (IVRS source) will be provided to compare the drug-related Grade 3 - 5 AE rate between the two treatment arms. Associated odds ratios and 95% CIs for Arm A relative to Arm B will be calculated. An estimate of the difference in rates (Arm A - Arm B) and corresponding 95% CI for the difference will be calculated using CMH methodology, adjusting for the same stratification factors.

Additional characterization of drug-related Grade 3-5 AEs will be provided, including summaries by system organ class (SOC) and preferred term (PT) during the entire treatment period and during the Part 1 treatment period and the Part 2 treatment period separately. These analyses are described further in Section 7.6.6.

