7.6.6 Adverse Events

See Core Safety SAP¹. Summaries of AEs and drug-related AEs will also be provided separately for events with onset during the Part 1 treatment period for All Treated Subjects and for events with onset during the Part 2 treatment period for All Subjects Treated in Part 2. These additional summaries by treatment period will be performed using the 30-day safety window only.

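### For subjects who start Part 2, AEs with onset more than 30 days after the last combination dose and before the first Part 2 dose (days 31-41 on schedule) are in neither by-period AE table

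*SAP*

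**What the plan says.** **Overall window.** SAP 6.1.2 counts an AE as on-treatment from the first dose of study treatment if it occurs "within 30 days (or 100 days depending on analysis) of the last dose of study treatment". It then adds: "The Post Baseline Period may be further divided into the following sub-periods".

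**Part 1.** SAP 6.1.2.1 runs from the first Part 1 dose and closes relative to the last Part 1 dose: "An AE will be counted as on-treatment during Part 1 if the event occurred within 30 days (or 100 days depending on analysis".

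**Part 2.** SAP 6.1.2.2 takes AEs "with an onset date-time on or after the date-time of the first dose of Part 2 study treatment". SAP 6.1.1 treats anything before that dose as a baseline event for Part 2.

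**Which window the period tables use.** SAP 7.6.6: "These additional summaries by treatment period will be performed using the 30-day safety window only".

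**What the period tables are for.** SAP 7.6.1 plans summaries of drug-related Grade 3-5 AEs "during the entire treatment period and during the Part 1 treatment period and the Part 2 treatment period separately", as further characterization of the primary result, and refers to 7.6.6 for detail.

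**Primary endpoint.** SAP 4.1 counts events "with onset on or after the first dose of study treatment and within 30 days of the last dose of study treatment", meaning any study treatment in either part.

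**Time between the parts.** Protocol 4.5: "The first flat dose 480 mg nivolumab in Part 2 will be administered 6 weeks after the last combination dose in Part 1". Protocol 4.3.2 gives the same 6 weeks.

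**The concern.** Taken together, these rules close Part 1 before Part 2 opens. For a subject who goes on to Part 2, the days in between are on-treatment overall but belong to neither sub-period.

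A subject whose only drug-related Grade 3-5 AE starts in that interval is in the primary numerator and in the entire-period table, yet in neither period table. A subject with another qualifying event in Part 1 or Part 2 still appears. A reader who sets the three tables side by side could therefore find primary-endpoint subjects missing from both parts, and the SAP gives no explanation.

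The affected subjects are those whose dosing continued, but this does not limit the interval to mild events. Protocol 4.4.4 does not require discontinuation for every drug-related Grade 3 or 4 event. Grade 3 endocrinopathies controlled with physiologic hormone replacement are one example, and isolated Grade 4 lipase or amylase abnormalities without signs of pancreatitis are another. Timing by part is also of interest in its own right, because the two arms differ only in Part 1.

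**Working it through.** **Check of the 6-week interval against the protocol's calendar.** Take the first dose as study day 1. Cycle 4 falls on day 1 + 3 × 21 = 64. Adding 42 days puts Cycle 5 on day 106, and (106 − 1)/7 = 15 completed weeks, so this is the first day of Week 16. That agrees with the note to protocol Table 5.5.1-1. Protocol 5.3 instead places Cycle 5 at Week 18. The two places must be reconciled, but the gap exists under either.

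**Gap.** Let day 0 be the last combination dose and day *d* the first Part 2 dose.

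- Part 1 under the 30-day window covers onsets up to day 30 (SAP 6.1.2.1, 7.6.6).
- Part 2 covers onsets from the dose on day *d* (SAP 6.1.2.2).
- Whole days in neither part: 31 to *d* − 1, which is *d* − 31 days.
- Time from first dose to Cycle 5, with four combination doses on schedule: 63 + *d* days.

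| Case | *d* | Days in neither part | Share of *d* | Share of 63 + *d* |
|---|---|---|---|---|
| 3 days early, if the ± 3 days in protocol 4.3.2 applies to Cycle 5 | 39 | 8 | 8/39 = 20.5% | 8/102 = 7.8% |
| On schedule | 42 | 11 | 11/42 = 26.2% | 11/105 = 10.5% |
| 3 days late (not a delay under SAP 7.4.2.1) | 45 | 14 | 14/45 = 31.1% | 14/108 = 13.0% |

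The early case is conditional: protocol 4.3.2 attaches ± 3 days to the 4-weekly dosing, then speaks only of dosing up to 3 days after the scheduled date. If Week 18 is read as the first day of that week, it is study day 17 × 7 + 1 = 120, so *d* = 120 − 64 = 56 and the gap is 25 days.

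**Longer delays.** Each further day adds one day to the gap. Protocol 4.4.4 limits this: an event-driven delay of more than 6 weeks from the previous dose requires discontinuation unless a listed exception applies, and the medical monitor must be consulted before treatment restarts. The listed exceptions are prolonged steroid tapers for drug-related AEs and approved delays for reasons that are not drug-related. Protocol 4.4.3 has a similar 6-week rule.

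**The 100-day option.** With a 100-day Part 1 window the gap would be zero, but days 42 to 100 (100 − 42 + 1 = 59 days) would lie in both parts. SAP 7.6.6 excludes this option for the period tables in any case.

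**Who is affected.** If a subject never starts Part 2, the last Part 1 dose is the last dose of study treatment. The overall and Part 1 windows then close on the same day and nothing is lost. If a subject starts Part 2 after day 31, the overall window is the Part 1 window, the residual interval and the Part 2 window end to end. The residual interval is therefore the only part of the primary-endpoint window outside both period tables.

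**The case against.** The strongest reply is that no planned inference depends on these tables. SAP 7.1 confines formal testing to the primary endpoint, and the events stay in the primary numerator and the entire-period summary. This stands, and it is why the point is minor.

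Nor does the SAP say that the two parts exhaust the post-baseline period. Subject counts would not add up even without the gap, because a subject with events in both parts is in both tables. A fixed 30-day window matches the primary endpoint's own post-dose window and avoids a Part 1 period whose length depends on delays for toxicity. All of this stands, and it argues for leaving the windows alone. It does not explain where events in the interval are shown.

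SAP 6.1.1 does give these events a status, as Part 2 baseline events. That label creates no summary of them, but any fix must be consistent with it.

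The Core Safety SAP and the Data Presentation Plan were not available, so a footnote or onset display there cannot be excluded. The study SAP sets the period definitions itself, however, and presents these tables as additional to the Core Safety SAP.

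A reader might infer more than the documents support:

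- **That the primary endpoint misses these events.** It does not; its window spans both parts.
- **That the events belong to Part 1.** The note to protocol Table 5.5.1-1 describes Part 1 as the first 12 weeks. On schedule that ends 84 − 63 = 21 days after the fourth dose, so the 30-day window already runs 9 days past it.
- **That one arm is favoured, or that many events are lost.** The documents give no distribution of onset times. The percentages above are shares of calendar time, not of risk or events.
- **That delays can widen the gap freely.** The 6-week rule and its exceptions limit this.

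**Conclusion.** The point holds as a minor one. For subjects who start Part 2, the by-period AE summaries leave out onsets on days 31 to 41 after the last combination dose when dosing is on schedule: 11 days, about a quarter of the 42-day interval. The figure is 14 days if Cycle 5 is 3 days late, and 8 if it may be and is 3 days early. Drug-related Grade 3-5 AEs in that interval count in the primary endpoint and the entire-period table but have no period table.

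This rests on reading the 30-day limit as onset date minus last dose date of at most 30, and on nothing in the unavailable documents overriding the study SAP. The effect is confined to descriptive outputs. The primary test, its alpha and its power do not change, and neither an event count nor a between-arm bias is claimed.

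**What to change.** Keep the Part 1 and Part 2 windows as written, and make three additions.

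1. In SAP 6.1.2 and 7.6.6, define the residual interval for All Subjects Treated in Part 2: onset more than 30 days after the last Part 1 dose and before the date-time of the first Part 2 dose. If the time is missing, an onset on the day of the first Part 2 dose stays in Part 2, as 6.1.2.2 already provides. State that the interval is consistent with the Part 2 baseline definition in 6.1.1.
2. In the by-period output, add one descriptive row or short table by arm. It should give the number of subjects with AEs, drug-related AEs and drug-related Grade 3-5 AEs starting in the interval, and the number of primary-endpoint subjects who appear in neither period table. Mark it as description only, because subjects who reach Part 2 are a post-randomization subset.
3. Footnote the Part 1 and Part 2 tables to say where these events are shown.

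The cost is SAP wording, one derivation, one small display and two footnotes. No new data are needed, and the primary analysis does not change. The downside is a display that may be sparse.

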6.1.2.2 Part 2 Treatment Period (Maintenance Portion)

Part 2 dosing is defined as any medication recorded on 'Record of Study Medication' CRF page with a visit label containing the text 'Part 2' and with total dose delivered > 0 mg.

On-treatment AEs during the Part 2 Treatment Period will be defined as AEs with an onset date-time on or after the date-time of the first dose of Part 2 study treatment (or with an onset date on or after the day of first dose of Part 2 study treatment if time is not collected or is missing). An AE will be counted as on-treatment if the event occurred within 30 days (or 100 days depending on analysis) of the last dose of Part 2 study treatment.

On-treatment evaluations (laboratory tests) during Part 2 will be defined as evaluations taken after the day (and time, if collected and not missing) of first dose of Part 2 study treatment. An evaluation will be counted as on-treatment if it occurred within 30 days (or 100 days depending on analysis) of the last dose of Part 2 study treatment.

6.2 Treatment Regimens

Arms A and B:

The treatment group **“as randomized”** will be retrieved from the IVRS system:

- Arm A (N3I1): Experimental arm: nivolumab 3 mg/kg + ipilimumab 1 mg/kg administered every 3 weeks for 4 doses followed by nivolumab flat dose 480 mg every 4 weeks
- Arm B (N1I3): Control arm: nivolumab 1 mg/kg + ipilimumab 3 mg/kg administered every 3 weeks for 4 doses followed by nivolumab flat dose 480 mg every 4 weeks

The treatment group **“as treated”** will be the same as the **“as randomized”** as long as the subject received at least one dose of study medication.

Cohort C:

All subjects will be assigned nivolumab 6 mg/kg + ipilimumab 1 mg/kg administered every 8 weeks alternating with a flat dose of 480 mg nivolumab every 8 weeks. The treatment group **“as treated”** will be the same as the assigned treatment as long as the subject received at least one dose of study medication.

6.3 Populations for Analyses

Since the primary objective will be addressed by a safety endpoint, the primary endpoint analysis will be based on all treated subjects. For consistency, the secondary endpoints will use the same analysis population as the primary endpoint (ie, all treated subjects).

Arms A and B:

- All Enrolled Subjects: All subjects who signed an informed consent form and were registered into the IRT.
- All Randomized Subjects: All subjects who were randomized to any treatment group. This is the primary dataset for efficacy listings
- All Treated Subjects: All subjects who were randomized to Arm A or Arm B and received at least one dose of any study medication. This is the primary dataset for analysis of study conduct, study population, efficacy (including secondary endpoints), exposure, and safety (including primary endpoint).
- All Subjects Treated in Part 2: All subjects who were randomized to Arm A or Arm B and received at least one dose of study medication in the open-label nivolumab flat dose maintenance phase (Part 2).
- Response-Evaluable Subjects: All treated subjects with measurable disease at a baseline tumor assessment and at least one on-treatment tumor assessment.
- PK Subjects: All treated subjects with available serum time-concentration data.
- Immunogenicity Subjects: All treated subjects with available ADA data.
 - Nivolumab ADA Evaluable Subjects: all treated subjects with baseline and at least 1 postbaseline nivolumab immunogenicity assessment.
 - Ipilimumab ADA Evaluable Subjects: all treated subjects with baseline and at least 1 postbaseline ipilimumab immunogenicity assessment.
- Biomarker Subjects: All treated subjects with available biomarker data.

- All PD-L1 tested subjects: Treated subjects who had a tumor biopsy specimen assessed for PD-L1 expression. This will be used for analyses of PD-L1 expression
- All PD-L1 evaluable subjects: All PD-L1 tested subjects with quantifiable PD-L1 expression
- Biomarker Evaluable Subjects: All Treated Subjects with a baseline measurement and at least one post-baseline sample for the given marker.

Cohort C:

- All Treated Subjects: All subjects who enrolled into Cohort C and received at least one dose of any study medication.
- All Enrolled Subjects, Response Evaluable Subjects, PK Subjects, Immunogenicity Subjects, and Biomarker Subjects are defined the same as for Arms A and B above.

7 STATISTICAL ANALYSES

7.1 General Methods

Unless otherwise noted, the following subsections describe tabulations of discrete variables, by the frequency and proportion of subjects falling into each category, grouped by treatment (with total). Percentages given in these tables will be rounded and, therefore, may not always sum to 100%. Continuous variables will be summarized by treatment group (with total) using the mean, standard deviation, median, minimum and maximum values. If a missing category is not being presented in the data display, only those subjects with non-missing values for the parameter being assessed are included in the percentage calculation.

Time to event distribution will be estimated using Kaplan Meier techniques. This will be done for endpoints progression free survival, overall survival and duration of response (note that TTR will be analyzed using summary statistics such as mean, SD, median, min, max). Median survival time along with 95% CI will be constructed based on a log-log transformed CI for the survivor function $S(t)^{4,5}$. Rates at fixed time points will be derived from the Kaplan Meier estimate and corresponding confidence interval will be derived based on Greenwood formula⁶ for variance derivation and on log-log transformation applied on the survivor function $S(t)^7$.

Confidence intervals for binomial proportions will be derived using the Clopper-Pearson method⁸.

Formal hypothesis testing with control of Type I error will only be conducted for the primary endpoint. In addition, descriptive analyses of secondary efficacy endpoints will be performed to evaluate the hypothesis of similar efficacy between the treatment arms A and B. The P-values and confidence intervals for these secondary analyses are for descriptive purposes only and will not be adjusted for multiplicity.

Subjects in Cohort C will not be included in the primary analysis and will be evaluated descriptively in a separate report.

7.2 Study Conduct

7.2.1 Accrual

The accrual pattern will be summarized per country, investigational site, and per month for all randomized subjects (Arms A and B) and for all treated subjects (Cohort C). Randomization date (if applicable), first dosing date, country, investigational site will be presented in a by subject listing of accrual.

Furthermore, the accrual pattern will be summarized by the stratification factors PD-L1 status and M Stage.

7.2.2 Relevant Protocol Deviations

The following programmable deviations will be considered as relevant protocol deviations and summarized by treatment group and overall. Non-programmable relevant eligibility and on-treatment protocol deviations, as well as significant (both programmable and non programmable) eligibility and on-treatment protocol deviations will be reported through ClinSIGHT listings.

At Entrance:

- Subjects with baseline ECOG performance status > 1
- Subjects who received prior systemic anti-cancer treatment in the metastatic setting
- Subjects without histologically documented Stage III or Stage IV melanoma, as per AJCC staging system

On-study:

- Subjects receiving anti-cancer therapy (chemotherapy, hormonal therapy, immunotherapy, standard or investigational agents for treatment of cancer) while on study therapy

Listings will also be provided.

7.3 Study Population

Summaries of study population will be based on all treated subjects, except that of subject disposition which will be based on all enrolled subjects.

7.3.1 Subject Disposition

For Arms A and B the total number of subjects enrolled (randomized or not randomized) will be presented along with the reason for not being randomized. This analysis will be performed on the all enrolled population only. For Cohort C the total number of subjects enrolled (treated or not) will be presented along with the reason for not being treated.

Number of subjects who discontinued study treatment along with corresponding reason will be tabulated by treatment group as treated. Reason for discontinuation will be derived from subject status CRF page. This analysis will be performed on the population of All Treated Subjects as well as the population of All Subjects Treated in Part 2.

For Arms A and B number of subjects randomized but not treated along with the reason will be tabulated by treatment group as randomized. This analysis will be performed on the all randomized population only.

A subject listing for all randomized subjects (Arms A and B) and for all treated subjects (Cohort C).will be provided showing the subject's randomization date (if applicable), first and last dosing date, off study date and reason for going off-study. For Arms A and B a subject listing for subjects not randomized will also be provided, showing the subject's race, gender, age, consent date and reason for not being randomized.

